Target number of participants	We anticipate to recruit 800 participants for this study over the course of 4 years

Criteria for evaluation	
Primary outcome measure(s): The primary outcome of the study is to evaluate if specific heritable arrhythmic disorders are associated with changes in selected protein distribution/expression levels at cell-cell junctions within the buccal mucosa. Our preliminary studies suggest that protein distribution/expression alterations in the buccal mucosa mirror equivalent changes that occur in the myocardium of patients with ACM. This study will evaluate the use of this "novel diagnostic tool" in individuals at risk of sudden cardiac death due to other, more common forms of arrhythmic disorders including the cardiac channelopathies. The processing approach (laboratory technique: immunocytochemistry) for protein distribution visualization has been optimized to be qualitative rather than quantitative. In this sense - each sample will be characterized by "presence" or "absence" of a specific protein at the cell-cell connections. We deem that the qualitative approach is not subject to bias and will ensure accuracy and reproducibility of the results.
 
Secondary outcome measure(s): A potential secondary outcome of the research is whether we can correlate protein distribution in the buccal mucosa with specific genotypes. Our preliminary results on the cohort of patients with ACM suggest that mutations in different genes result in different protein distribution patterns within the buccal mucosa. Being able to predict the gene bearing the disease-causing mutation will significantly reduce the time and cost of genetic sequencing. Identifying the specific gene underlying a heritable arrhythmic disorder is of pivotal importance as increasingly developing genotype/phenotype correlations help individualized risk identification and patient management.
 
Another potential secondary outcome of the research has to do with the effect changes in the patients' treatment plans may have on protein distribution. An example has to do with a protein known as Connexin43 (Cx43). Cx43 is the major gap junction protein expressed in the heart and is responsible for the electrical coupling of the cells and the smooth propagation of electricity throughout the myocardium. Cells at the buccal mucosa also express Cx43. It has been shown that patients with arrhythmic disorders show decreased distribution of Cx43 at the cell borders in their hearts and this "Cx43 remodeling" has been associated with an increased risk for arrhythmias. Our preliminary studies show that patients with ACM, as well as patients with different types of cardiomyopathy (including dilated, hypertrophic and ischemic) show Cx43 remodeling in their buccal mucosa. If a patient shows Cx43 remodeling during initial sampling and in a follow-up visit his clinical care team deems necessary to change his treatment plan (for instance, if he/she is to be started on a different anti-arrhythmic drug) we would like to study Cx43 distribution again during one of his/hers follow up visits. If the new treatment plan results in restoration of Cx43 at the buccal mucosa cell connections, and given how protein distribution in the buccal epithelium mirrors protein distribution in the heart, this finding may be an indication of successful arrhythmia management. It could thus, potentially, provide us with a non-invasive, straightforward and risk-free means to assess therapy efficacy in the future.

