9.3 Definition of the End of Trial

We define the End of the Trial as the day when the last buccal cell sample is obtained and analysed from a volunteer.

Study Procedures

Screening assessments

Participants will fall in either of the following three categories:

1. Patients already diagnosed with a heritable arrhythmic disorder (ACM, hypertrophic cardiomyopathy, dilated cardiomyopathy, Brugada syndrome, Long QT syndrome, catecholaminergic polymorphic ventricular tachycardia). The individuals will only be asked to participate in the study based on their already established diagnosis. No baseline screening assessment will be required.
2. Family members of patients diagnosed with a specific heritable arrhythmic disorder regardless of whether they show disease manifestation or not. These individuals will be asked to participate in the study based on the diagnosis of the proband. No further screening assessment will be required.
3. Family members of SCD victims. If pathology examination of the SCD victims' heart suggests that the individual has died due to a heritable arrhythmic disorder, when his/her family members attend the arrhythmic services at City St George's, University of London for medical evaluation/ risk stratification, they may be asked to participate at the study regardless of whether they show evidence of disease manifestation. No further screening will be required other than the clinical screening that is regularly offered to SCD victim relatives for risk stratification.

Baseline assessments

No baseline assessments are required after the participant has entered the study.

Interventions

The study participants will just be asked to open their mouth. A study team member will rub a soft brush a few times at the inside of their cheek and smear the brush on a microscopy slide. The slide will be sprayed with 70% ethanol to preserve the material and taken to the research laboratory. The patient will have a total of 6 smears taken (3 from each cheek). For the majority of the patients, only a single sampling will be enough which will take place during one of their regular follow-up appointments at the cardiology clinic. There is no pain and no discomfort associated with the procedure and it lasts only a few seconds.

If sampling is being done at-home, the participant will be provided with a kit containing two soft brushes, 6 microscopy slides, a small spray bottle with the fixative, and slide boxes. The

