buffer. For plakoglobin the optimal dilution is 1: 1500 and I use the mouse monoclonal antibody from sigma P8087. For Cx43 the optimal dilution is 1:1000 and the antibody is a rabbit polyclonal from Abcam ab11370. For desmoplakin the optimal dilution is 1: 50 and the antibody is a mouse monoclonal from Fitzgerald 10R-D109a. For PKP1 the optimal dilution is 1:20 and the antibody is a mouse monoclonal from santa cruz biotechnology sc-59880. Further protein targets/optimal dilutions will be assessed throughout the length of the study. The primary antibody stays on the slides overnight at 4 °C. The next day the slides will be equilibrated at room temperature for ~ 30 minutes, and washed 3 times (5 mins each) in PBS + 1% Triton-X. The secondary antibody is diluted in PBS (I use goat anti-mouse or anti-rabbit Cy3 conjugated antibodies from Jacksons ImmunoResearch at a dilution of 1:400) and the slides left in a covered box at room temperature for 2 hours. Following incubation with the secondary, again the slides are washed 3 times in PBS + 1% triton-X and mounted in mounting medium containing 4',6-Diamidino-2-Phenylindole, Dihydrochloride (DAPI).The immunostained slides will then be analysed by laser confocal microscopy at the Image Facility Core of City St George's, University of London.

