Regarding the secondary outcome of the analysis: patients with ACM bear mutations in genes encoding desmosomal proteins. These include desmoplakin, desmoglein2, desmocollin2, plakoglobin and plakophilin2 (PKP2). Buccal cells do not express PKP2. Instead they express a different isoform of the protein; plakophilin1 (PKP1). 15/15 ACM patients bearing mutations in PKP2 showed loss of PKP1 signal in their buccal mucosa. No patients bearing mutations in different genes showed this abnormality. Moreover, only patients bearing mutations in desmoplakin, desmoglein2 or desmocollin2 showed loss of desmoplakin signal in their buccal mucosa. Accordingly, using PKP1 distribution to predict the presence of mutations in PKP2 showed 100% specificity and sensitivity. This is a remarkable finding given how PKP1 and PKP2 are expressed by different genes localized on different chromosomes. And yet, a mutation in one

isoform expressed in one tissue affects distribution of a different isoform expressed in a different tissue. Similarly, using desmoplakin distribution to predict the presence of mutations in desmoplakin, desmoglein2 and desmocollin2 showed 100% specificity and sensitivity. We are now at a position to use the same approach in other, more common forms of arrhythmic disorders including the cardiac channelopathies.

We shall use the presence or absence of signal for specific proteins at buccal smears to:

1. predict clinical diagnosis for heritable arrhythmic disorders
2. predict the genes bearing disease-causing mutations
3. assess the effect of potential changes in treatment plan on the distribution of proteins (specifically Cx43)

We shall use the expression levels of specific proteins to establish

1. If mutations act through haploinsufficiency
2. If anti-arrhythmic medication corrects the distribution of connexin43 by increasing its production levels.

Sensitivity and other planned analyses (if applicable)

Please see explanation above

Interim analysis

If following the first year of the study, it appears that we are unable to predict "arrhythmic status" using such samples, we shall stop recruiting patients with cardiac channelopathies and will only focus on patients with cardiomyopathies, where the correlation is already proved

Committees involved in the trial

A trial management group (TMG) will be in place throughout the duration of the study

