Identifiable		
*Pseudonymised		
Anonymised		

**Confirm that the key to this data is kept securely away from the used data with strict controlled access*

The key linking the study ID number to a specific participant will be held in secure workstations at or Bart's Hospital, only accessible by the participant's regular medical team.

List all organisations / agencies which will have access to the personal data collection used for this project / process

Only the regular medical care providers of each participant will have access to the participants' personal data. No personal data will be collected for the purpose of this study.

Length of the study – include an assessment of the necessity and proportionality of the processing in relation to the purpose. Also include who, internally & externally, has been consulted in the preparation of this DPIA.

The current end date of the study is 30/06/2026. All eligible participants have regular follow-up appointments every 6 or 12 months. In order for us to recruit enough participants for the study's outcomes to reach statistical significance, at least 1 year is required.

[name], the City St George's, University of London representative has been consulted for the preparation of this DPIA.

If external organisations / agencies are involved, is there a contract or information sharing agreement in place with suitable clauses for data protection and data incident reporting.? If not why not?

Not applicable.

RISK

Can you achieve your objectives using anonymised data? – see ICO Code of Practice on Anonymisation

Yes	X	
No		Why not?

What are the benefits to the individual of their personal data being used for this purpose?

Not applicable

What are the organisational benefits of the individual's personal data being used for this purpose?

Not applicable

What are potential negative impacts to the individual of their personal data being used for this purpose in the event of a Data Breach occurring?
 
Not applicable
											

How will you avoid causing unwarranted or substantial damage/distress to the individual when using their personal data for this purpose?
 
Not applicable
											

Is the data already held by City St George's?
 
 
 Yes	X		
 
 No			
 
				Yes	X			No			

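### The before-and-after Cx43 comparison has no run control, same-run re-staining, paired analysis or comparator without treatment change, so a false absent call on the first smear can appear as restoration

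*Combined protocol and SAP*

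**What the plan says.** The synopsis (section 3, Criteria for evaluation) describes the treatment-change outcome through a Cx43 example. The starting point is "If a patient shows Cx43 remodeling during initial sampling". If treatment is later changed, "we would like to study Cx43 distribution again during one of his/hers follow up visits". It then says: "If the new treatment plan results in restoration of Cx43 at the buccal mucosa cell connections", this may indicate successful arrhythmia management and could in future become a way to judge therapy.

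The Secondary endpoint analysis lists the same aim, to "assess the effect of potential changes in treatment plan on the distribution of proteins (specifically Cx43"), without naming a test, denominator or comparator. The Primary endpoint analysis names only pairwise Fisher exact tests between disease groups. Section 14.2.1 makes each stain a present or absent call and rules out quantification.

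On timing, the data protection assessment (section 25) states: "All eligible participants have regular follow-up appointments every 6 or 12 months". Section 10.4 lets interim results from self-taken samples prompt an earlier appointment.

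On the laboratory side, section 10.5.1 says "For Cx43 the optimal dilution is 1:1000 and the antibody is a rabbit polyclonal from Abcam ab11370". It describes no control slide, run acceptance rule or reserved first-visit slide. The items listed for the data collection form in section 25 do not include staining run, antibody lot or dilution. Section 10.3 provides six slides per sampling, three from each cheek.

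**The concern.** In the synopsis example, a patient enters the comparison because the first call was abnormal. A patient whose Cx43 is truly present but was called absent can then either stay absent or move to present, and the second is what the synopsis would read as possible treatment success. With entry defined this way, error in the first call pushes in one direction only.

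If the error comes from a weak staining run, every patient stained in that run is affected together, so it does not average out across patients. A present/absent readout does not help, because a weak run is simply recorded as absent.

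The result matters beyond this outcome. Section 10.4 already describes Cx43 restoration under effective medication as something the group's smear work has shown. One aim of the Western blot sub-study is to explain how that restoration comes about.

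**Working it through.** The plan states no sample size, restoration rate or repeatability for this comparison, so there is no figure to reproduce. The check has two parts.

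**Are the two slides stained in different runs?** The synopsis requires the first smear to have been read before the patient qualifies. The second is taken at a later follow-up visit, with visits 6 or 12 months apart (section 25). Section 10.4 uses interim results, which implies that samples are read as they come in. Different runs are therefore a strong inference, but not stated text.

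**How much apparent restoration can arise with no true change?** All inputs here are assumptions:
- *r*: share of patients whose Cx43 is truly absent (taken as what remodelling means in a present/absent readout)
- *w*: chance that a truly present signal is called absent, equal and independent at the two readings
- no false-present calls

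Share called absent first = r + (1−r)w.

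Apparent restoration among them = (1−r)·w·(1−w) / [r + (1−r)w].

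| r | w | Numerator | Denominator | Apparent restoration |
|---|---|---|---|---|
| 0.7 | 0.1 | 0.3×0.1×0.9 = 0.027 | 0.73 | 4% |
| 0.5 | 0.1 | 0.5×0.1×0.9 = 0.045 | 0.55 | 8% |
| 0.3 | 0.1 | 0.7×0.1×0.9 = 0.063 | 0.37 | 17% |
| 0.5 | 0.2 | 0.5×0.2×0.8 = 0.080 | 0.60 | 13% |
| 0.8 | 0.02 | 0.2×0.02×0.98 = 0.0039 | 0.804 | 0.5% |

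**A weak first run.** Let the false-absent rate be f1 in the first run and 2% in the second, with a 5% false-present rate and r = 0.5. For f1 = 20%:
- Called absent first: 0.5×0.95 + 0.5×0.20 = 0.575
- Of all patients, moving to present: 0.5×0.95×0.05 + 0.5×0.20×0.98 = 0.122
- Apparent restoration: 0.122/0.575 = 21%

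The same calculation gives 14% at f1 = 10% and 37% at f1 = 50%.

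**Does comparing everyone solve it?** Only in part.
- With equal error in both runs (r = 0.5, 10% false-absent, 5% false-present), gains and losses both equal 0.5×0.95×0.05 + 0.5×0.10×0.90 = 6.9% of all patients, so the effect of selection cancels.
- With the weak first run above, gains are 12.2% and losses are 0.5×0.05×0.95 + 0.5×0.80×0.02 = 3.2%. The run effect remains and needs same-run staining, run controls, or a no-change group stained in the same runs.

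**What does a held first-set slide achieve?** If it is stained with the follow-up slide and both first-set calls must be absent, the restored cases are a subset of those counted before, so none can be added. Ageing limits the benefit. At r = 0.5 and w = 0.1, suppose half of aged normal slides read absent. The numerator falls to 0.5×0.1×0.5×0.9 = 0.0225. Divided by 0.55 (first call absent) this is 4.1%; divided by 0.5 + 0.5×0.1×0.5 = 0.525 (both first-set calls absent) it is 4.3%. So 8% falls only to about 4%.

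**The case against.** A reader might infer four stronger things that the documents do not support.

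- *Only patients with an abnormal first smear are compared.* That is the synopsis example. Section 10.4 asks all participants for further samples whatever the baseline result, and section 5.2 and the Secondary endpoint analysis state the aim without selecting on the first call. Sections 6.2 and 10.3, on the other hand, say one sampling is enough for most. These sections conflict, so a settled one-sided design cannot be claimed.
- *Staining run is fully confounded with treatment.* If the section 10.4 sampling is carried out, a patient may have several samples before and after a change. Runs could then mix changed and unchanged patients, and one weak run might show as an isolated call.
- *The Cx43 dilution will drift.* The sentence "Further protein targets/optimal dilutions will be assessed throughout the length of the study" most naturally concerns new targets; Cx43 has a named antibody and a stated dilution.
- *Runs are known to fail.* No run failure, lot change or repeatability problem is reported.

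The outcome is also described as potential and its interpretation is hedged. Section 14.2.2 lists no secondary endpoints.

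All of this stands and limits the claim. It does not remove it: data for a two-way comparison may exist, but no such analysis is named, and nothing described separates a run effect from a treatment effect.

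**Conclusion.** The point holds as a possible bias, not a demonstrated one. Followed as the synopsis describes it, the comparison lets a false absent first call count as restoration, and selecting on that call fixes the direction of the error.

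Its size is unknown. It is about 4% to 17% with a 10% false-absent rate and a true remodelling share of 70% down to 30%, and 13% at a 50% share and a 20% rate. Both assume no treatment effect and no false-present calls. It is 0.5% in a favourable case and 37% with a very weak first run at a 50% share. Without a Cx43 repeatability figure, the sponsor could not tell these cases apart. Separate runs remain an inference, though a strong one. The matter concerns a potential secondary outcome, so it is a worthwhile, cheap improvement and does not affect the primary comparison between disease groups.

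**What to change.** 1. In section 10.5.1 and the Secondary endpoint analysis, hold one fixed, unstained slide from the first set where the six slides allow. After a treatment change, stain it for Cx43 in the same run, with the same antibody lot and dilution, as the follow-up slide. Count a patient as restored only if the first call and the re-stained first-set slide are both absent and the follow-up slide is present.
2. Record run, lot and dilution with each call.
3. Using the repeat samples that section 10.4 already requests from all participants, report changes in both directions with a paired analysis (for example McNemar), alongside re-sampled participants without a treatment change.
4. Reconcile the synopsis, sections 5.2, 6.2, 10.3 and 10.4, and the Secondary endpoint analysis on who is re-sampled and who is compared.

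**Cost.** Treatment changes cannot be foreseen, so a slide is withheld from each participant. Section 10.5.1 names four proteins; if each takes one slide, which is an assumption, two remain, and added targets could use them. The planned 4 °C storage is for slides after imaging, so storage of unstained slides must be added. One extra slide is stained per treatment-change participant. Signal loss over the usual 6 to 12 months weakens the check, but cannot add false restorations. No single residual error rate can be quoted, because the held and follow-up slides share a run and their errors are not independent.
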